#### **Calendar of Events**

#### Data Collection and Management -

Data collection will occur at each visit outlined in the **Calendar of Events**. All study data will be recorded on data collection forms (CRFs: Case Report Forms) designed by the research manager ([name], MS, PhD), and securely maintained. Any discrepancies between data collection forms and supporting source documents such as physician's notes should be explained on the forms. Any changes made to original entries on data collection forms should be crossed through with a single line and initial and dated by the person making the correction. Do not obscure the original entry.

Data will be entered by study manger's staff into a REDCap Database (described in detail in the "STUDY SUBJECT PROTECTION" section of this protocol) that will be stored on a secure server by the study center (WF: Wake Forest University). Study data source documentation and progress notes will be monitored by the PI (principal Investigator) as outlined in the "STUDY MONITORING AND DOCUMENTATION" section. Data collected from visits should be entered into REDCap within 5 business days. Any queries to data entered into REDCap should be addressed within 5 business days.

WF site will maintain all essential study documents in original format and source documentation that support the data collected on study participants in compliance with ICH/GCP guidelines. Documents must be retained until at least 2 years have elapsed

since the formal discontinuation of the clinical investigation. Research Center WF Urology Female Pelvic Health Group PI will be responsible to ensure that these essential documents are retained and are not accidentally damaged or destroyed prior to the required elapsed time.

### Study Monitoring and Documentation

#### Study Monitoring

The PI at the WF center will monitor the study and assess the need for amendments as the study progresses. If a protocol revision is necessary for reasons including but not limited to the rights, safety, or welfare of participants, or scientific integrity of the data, an amendment is required. IRB (Institutional Review Board) or equivalent approvals of the revised protocol—and if necessary, revised informed consent—must be obtained prior to implementation at each site.

#### Data Monitoring

Semi-annual data verification will be conducted by the research manager to verify that data entry into REDCap is accurate, and to assess compliance with the study protocol requirements. Study data will be source-verified for roughly 25% of overall data collection efforts. Progress notes and supporting documents will be obtained from the EPIC WakeOne within 3 days of procedure and scheduled visits. Other monitoring activities include but are not limited to reviewing informed consent/research authorization forms, adverse event documentation, and protocol deviation reports.

# **Protocol Deviations -**

Protocol deviations will be documented in sequential order according to event of occurrence and they will be entered into REDCap.

# **Reporting Adverse Events:**

In a study by Kaplan, AE's in women and children were abdominal pain, asthenia, constipation, dizziness, dry mouth, drowsiness, dyspepsia, headache, incontinence, nasal congestion, nausea, orthostatic hypotension, and somnolence.

The overall safety profile in women seemed to be generally consistent with the profile in men.

Patients will initially be screened for these adverse events on postoperative day 1 via telephone call.

Adverse events (AEs) will be recorded and reported to local IRB as per regulations on Serious Adverse Event reporting guideline. Post-operative and surgical attributed AEs will be defined using the Clavien-DINDO grading

TABLE 1. Classification of Surgical Complications Clavien-DINDO Grade Definition for surgery attributed post-op events only

Grade 1	Any deviation from the normal postoperative course without the need for pharmacologic treatment. Allowed therapeutic interventions are: drugs as antiemetics, antipyretics, analgesics, physiotherapy
Grade II	Requiring pharmacological treatment with drugs other than such allowed for grade I complications Blood transfusions and total parenteral nutrition are also included
Grade III	Requiring surgical, endoscopic or radiological intervention Intervention not under general anesthesia
IIIA IIIB	Intervention under general anesthesia
Grade IV	Life-threatening complication (including CNS complications)* requiring IC/ICU management
IVA	Single organ dysfunction (including dialysis)
IVB	Multi-organ dysfunction
Grade V	Death

Protocol Specific Reportable AEs include those determined to be related to postoperative recovery as listed below:

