The purpose of this double-blind, randomized controlled trial is to determine the difference in incidence of POUR following a postoperative day 0 voiding trial in patients undergoing multicompartment native tissue vaginal repair of pelvic organ prolapse, with or without concomitant mid-urethral sling, who received 0.4 mg of tamsulosin 5 days pre- and post-operatively compared to those who receive placebo. The 5-day period was determined based on the pharmacokinetics of tamsulosin. Given the recent trend in

same-day discharge, increasing the success of postoperative day 0 voiding trial would theoretically decrease the percentage of patients going home with indwelling Foley catheters, increase patient satisfaction and decrease urinary tract infection rates. Additionally, continuing tamsulosin for 5 days postoperatively to prevent decrease in steady-state blood levels may theoretically reduce the incidence of delayed urinary retention.

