#### Secondary:

To compare the following between the two groups:

- 1. Postoperative urinary tract infection rates (up to 6 weeks post-surgery)
- Incidence of delayed urinary retention (defined as PVR > 150 ml up to 6 weeks post-surgery)
- 3. ED visits and serious adverse events within 30 days post procedure
- 4. Total number of days of catheterization
- 5. Patient level of satisfaction with voiding/bladder function immediately prior to hospital discharge: Very dissatisfied, moderately dissatisfied, slightly dissatisfied, neutral, slightly satisfied, moderately satisfied, very satisfied

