# Randomization -

All enrolled and consented patients will undergo randomization at their pre-operative clinic visit. A study patient can be randomized into either tamsulosin IP or Placebo IP group. Randomization assignment will occur through sealedenvelope.com-generated random allocation using a randomly permutated block design (8 subjects per block). An

unblended designated person who will not participate in data collection or analysis will be responsible for providing randomization schedule. Study staff will dispense the assigned IP bottle (see below) in the urology clinic. Study patient charts will get updated with the IP ID (e.g. 01A, 02A, 01B, 02B...). Research staff administering follow-up questionnaires will also be blinded to the subject's randomization. The subject will be asked to bring back their IP bottle at the time of their postoperative visit.

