#### Study Intervention –

10 pills of each IP and placebo will be placed in identical coded containers and stored in a locked area in the clinic. Instructions for IP usage will be provided to subjects for 10 days of usage as 0.4 mg qd by PO route starting 5 days prior to day of surgery and continued for a total 10 days. The research manager will be the only member of the study team who has the research key designating which containers are IP versus placebo.

On postoperative day 0 after recovery from anesthesia, each patient will have their bladder emptied using the indwelling Foley and their bladder will then be retrograde-filled with 300 cc of normal saline and given 30 minutes to void. A postvoid residual volume<150 cc will be considered a success of the voiding trial. If the voiding trial was considered failed, the patient will have a foley catheter reinserted and the patient will be instructed to remove the catheter at home after having a bowel movement. If they are unable to void at home within 4 hours of catheter removal, they will return to the Wake Forest Urology clinic for self-catheter teaching.

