# IP Accountability -

IP and placebo bottles will be stored in a locked cabinet on the clinic premises. They will be dispensed to the patient at the time of consent collection and will be brought back by the patient at time of the 1-week postoperative visit. This will be recorded in a study log to keep track of bottles signed in and out. The bottles as well as log will be stored for long-term archiving.

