# Postop parameters

- Active voiding trial PVR on POD 0
- Day of bladder function return
- UTI within 6 weeks
- Persistent urinary retention > 2 weeks
- Delayed urinary retention (PVR > 150 after passing 1st trial of void)
- Emergency Room visit/evaluation

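### The between-arm ED-visit and SAE count opens at surgery, so events during the first 5 of 10 planned doses are not compared by arm

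*Combined protocol and SAP*

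**What the plan says.** - **Order of events.** Under Randomization: "All enrolled and consented patients will undergo randomization at their pre-operative clinic visit". Under IP Accountability, on the study bottles: "They will be dispensed to the patient at the time of consent collection". Under Study Intervention, dosing is daily, "starting 5 days prior to day of surgery and continued for a total 10 days".
- **Outcome.** The Secondary outcomes list compares between groups "ED visits and serious adverse events within 30 days post procedure". The matching secondary aim gives no window, so this line sets it.
- **Data field.** Appendix A holds the ED visit as "Emergency Room visit/evaluation", under Postop parameters. No other ED field appears.
- **First check.** Under Reporting Adverse Events: "Patients will initially be screened for these adverse events on postoperative day 1 via telephone call". The Calendar of Events has no adverse event row and no contact between baseline and the day of surgery. Its day-of-surgery column lists only the voiding trial, PVR and satisfaction.
- **Other routes to a record.** Adverse Event Definitions sets no start time and does not require a relation to study drug. Data Monitoring adds: "Progress notes and supporting documents will be obtained from the EPIC WakeOne within 3 days of procedure and scheduled visits".

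**The concern.** In a placebo-controlled drug trial, the safety comparison should follow randomized women from their first dose. Here it starts at the operation. The days left out are those when drug and placebo differ but surgery and anesthesia cannot yet explain an event. Several symptoms on the protocol's Medication-related list (nausea, drowsiness, constipation, abdominal pain) are easy to blame on surgery once it has happened. The protocol's top category for relatedness requires that no other cause be apparent, which is easiest to judge before the operation, when no one is scheduled to ask.

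A randomized woman whose surgery is cancelled has no postoperative day 1 and no procedure from which to count 30 days. As written, she has taken study drug but has no place in this outcome.

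**Working it through.** **Inputs.** Ten daily doses, the first on day −5 (Study Intervention). Outcome window: 30 days from the procedure on day 0 (Secondary outcomes). First adverse event check: day +1 (Reporting Adverse Events). Enrollment: 44 per arm, 88 in total (Power analysis).

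**Step 1: count the doses.** Study Intervention reads as ten consecutive days. The Background describes women "who received 0.4 mg of tamsulosin 5 days pre- and post-operatively", which can be read as skipping the day of surgery. The two passages need to be reconciled, so both readings are counted.

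| Doses | Days −5 to +4 | Days −5 to −1 and +1 to +5 |
|---|---|---|
| Planned | 10 | 10 |
| Before the day of surgery | 5 | 5 |
| Before postoperative day 1 | 6 | 5 |
| Inside the current window | 5, or 4 if the day-0 dose precedes surgery | 5 |
| Inside a window from first dose | 10 | 10 |

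Both readings reproduce the plan's ten doses with five before the day of surgery.

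**Step 2: count the time.** First dose to 30 days after surgery is 5 + 30 = 35 days. The current window covers 30/35 = 86%; the part left out is 5/35 = 14%.

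**Step 3: trace one event.** Suppose a randomized woman visits the ED on day −3.
- No contact is planned before the day of surgery, and that visit lists no adverse event question.
- The day 1 call may bring out the symptom, and the chart pull may show the visit.
- If found, it meets the adverse event definition and can be recorded.
- It is still not within 30 days after the procedure, so it does not enter the between-arm count.

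**Step 4: what one event is worth.**
- One event in an arm: 1/44 = 2.3 percentage points.
- Fisher exact test, two-sided: 1/44 versus 0/44 gives p = 1.00; 2/44 versus 0/44 gives p = 0.49.
- With no events in an arm, the one-sided 95% upper limit is 1 − 0.05^(1/44) = 6.6%, whichever window is used.
- Each cancelled surgery removes 1/88 = 1.1% of randomized women from the outcome.

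The documents give no rate of pre-operative ED visits, SAEs or cancellations, so the expected number of uncounted events cannot be computed.

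**The case against.** The strongest reply is that a 30-day post-procedure window is a coherent choice for surgical recovery. It matches the 30-day readmission and reoperation fields in Appendix A and covers most of the follow-up time. The adverse event definition is open-ended. The day 1 call asks about drug symptoms six days after the first dose and is not limited to symptoms since surgery. The plan names no between-arm comparison of non-serious events, so a late symptom check does not itself bias a stated outcome. All of this stands, and it keeps the point small. It does not answer Step 3: an event that is recorded is still not one that the outcome counts.

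A reader might infer more than the documents support:
- *That pre-operative events are lost altogether.* They are not; they can be volunteered, recalled or found in the chart.
- *That half of the safety information is missing.* Half of the doses precede the window, but only 5 of 35 days do.
- *That a missed event is likely.* Any such probability would rest on an assumed rate that the documents do not supply.
- *That the Clavien-Dindo wording in the secondary aim removes drug-related SAEs.* The table in Reporting Adverse Events limits that grading to surgery-attributed events. No section limits which SAEs are counted on that ground.
- *That cancelled cases are a material loss.* No cancellation rate is given.

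**Conclusion.** The point holds as a gap in counting. As written, SAEs and ED visits during the first 5 of 10 planned doses fall outside the between-arm safety outcome, and no adverse event question is planned until postoperative day 1. This is the effect of a stated rule, not of missing detail.

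The expected effect on the comparison is small and cannot be estimated from the documents. The primary outcome and the sample size are untouched. The count of five doses holds under both readings of the dosing days; the 35-day figure assumes that the first dose is taken 5 days before surgery as planned. The case for change is complete counting by randomized arm at low cost, not statistical power.

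**What to change.** - **Secondary outcomes:** count ED visits and SAEs from first study dose to 30 days after surgery, by randomized arm and regardless of attribution. Report the pre-operative and 30-day post-procedure counts separately as well, so the usual surgical figure remains available.
- **Cancelled surgery:** for a randomized woman who does not have the operation, use 35 days from first dose (5 + 30).
- **Appendix A:** record each ED visit with its date, from first dose onward.
- **Calendar of Events:** at the existing day-of-surgery visit, before the operation, ask directly about ED visits, SAEs and the Medication-related symptoms. Leave out postoperative atrial fibrillation, which cannot yet have occurred. Keep the day 1 call, and show both checks in the calendar.

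The cost is some protocol wording, a few case report form fields at a visit that already exists, and one contact per cancelled case. A few more events may need to be filed, and precision does not improve.

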# Surgery or catheter-related:

Infection (UTI, Vaginal, Pelvic Abscess)

Venous Thromboembolism

Pelvic pain

Surgical bleeding (Significantly higher estimated blood loss)

Vaginal bleeding (Unexpected bleeding following sexual activity)

Excessive vaginal discharge

Fistula

New or worsening dyspareunia

Hematoma

Urgency 'de novo'

Stress or Urgency Incontinence (New or worsening)

Urinary retention (PVR>150) longer than 2 weeks post-surgery

#### Medication-related:

Orthostatic hypotension/dizziness Postoperative atrial fibrillation Abdominal pain Asthenia Constipation Dry mouth Drowsiness Dyspepsia Headache Nasal congestion Nausea Somnolence

Underlying diseases are not reportable as AEs unless there is an increase of severity or frequency during the course of the study. If an AE has not resolved at the time of AE Form completion, save form as incomplete in REDCap until resolved. Once resolved, update AE form, and enter into REDCap and save form as complete.

# Adverse Event Definitions:

Adverse Event: any untoward medical occurrence, unintended disease or injury, or any untoward clinical signs (including abnormal laboratory finding) in subjects, whether or not related to the administration of IP versus placebo.

Serious Adverse Event: an adverse event that Led to death

Led to serious deterioration in the health of the subject that either resulted in

- a life-threatening illness or injury
- a permanent impairment of a body structure or a body function in subject or prolonged hospitalization of existing hospitalization
- medical or surgical intervention to prevent life-threatening illness or injury or permanent impairment to a body structure or a body function

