# Secondary Aim(s):

- To compare the mean total number of days of postoperative catheterization, incidence of delayed urinary retention and urinary tract infection rates up to 6 weeks post-surgery between groups
- (2) To compare ED visits and serious adverse events, as classified by Clavien-Dindo, between groups
- (3) To compare patient level of satisfaction with voiding function immediately prior to hospital discharge and at 1 week post-procedure.

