#### Inclusion criteria:

- 1. Stage II or greater pelvic organ prolapse in > 1 vaginal compartment
- 2. Plan for multicompartment native tissue vaginal repair (which would include any combination of uterosacral ligament suspension, sacrospinous ligament suspension, cystocele and/or rectocele repair, with or without hysterectomy and with or without concomitant mid-urethral sling) or vaginal closure with FPMRS-trained surgeons at Wake Forest Baptist Health.
- 3. Participation in Enhanced-Recovery-After-Surgery protocol with plan for sameday hospital discharge
- 4. Willing to remain compliant with IP.

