# - Readmission within 30 days

- Reoperation for complication within 30 days

- Other (including: Delayed urinary tract injury, Delayed bowel injury, Hematoma, Transfusion, Cardiac complication, Respiratory complication)

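### The serious adverse event definition counts a prolonged hospital stay but not a new admission, in a trial built on same-day discharge

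*Combined protocol and SAP*

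**What the plan says.** The combined protocol and SAP defines an SAE once, under Adverse Event Definitions. Apart from death, an event must first satisfy a stem, "Led to serious deterioration in the health of the subject that either resulted in", and then one of three results. The first is a life-threatening illness or injury. The second is "a permanent impairment of a body structure or a body function in subject or prolonged hospitalization of existing hospitalization". The third is "medical or surgical intervention to prevent life-threatening illness or injury or permanent impairment to a body structure or a body function". The second is the only one that mentions hospital.

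Four other places bear on the point:

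- Inclusion criteria, item 3, requires "Participation in Enhanced-Recovery-After-Surgery protocol with plan for sameday hospital discharge".
- Outcomes, Secondary, item 3, compares "ED visits and serious adverse events within 30 days post procedure". Secondary Aim 2 states the same comparison with a classification: "To compare ED visits and serious adverse events, as classified by Clavien-Dindo, between groups".
- Reporting Adverse Events says: "Adverse events (AEs) will be recorded and reported to local IRB as per regulations on Serious Adverse Event reporting guideline". The guideline is not named and its text is not given.
- Appendix A lists "Readmission within 30 days" among the variables to collect. Readmission appears in neither the SAE definition nor the list of outcomes.

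**The concern.** The hospital criterion needs a stay that is already under way. In this trial the index stay is planned to end on the day of surgery, while the study drug runs for 10 days starting 5 days before surgery, and follow-up continues to 6 weeks. Most of the drug exposure and nearly all of the follow-up therefore take place when the woman is at home and there is no stay to prolong.

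The protocol's own lists of reportable events include some that could lead to admission after discharge: pelvic abscess and hematoma on the surgical side, orthostatic hypotension and atrial fibrillation on the medication side. Whether such an event is serious should depend on how ill the woman became. As written, it can depend on whether she had already gone home. At stake are the completeness of a compared secondary outcome and a clear rule for staff who must decide what is serious.

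**Working it through.** The plan states no figure for this point, so there is none to reproduce. The check is to apply the definition as worded, then to bound the number of women involved.

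**Step 1. Apply the definition.** Take an adverse event with serious deterioration that is not fatal, not life-threatening, not permanently impairing and not treated to prevent such harm. Only the hospital criterion can then make it serious.

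| When the event occurs | Effect on hospital stay | SAE as written? |
|---|---|---|
| On study drug, before surgery | New admission | No |
| Day of surgery, before discharge | Index stay extended | Yes |
| After same-day discharge | New admission | No |
| During a later admission | That stay extended | Yes |

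The second and third rows can describe the same deterioration at different times. The fourth row is why the criterion operates almost only, rather than only, around the day of surgery. The first row lies outside the secondary outcome, which starts at the procedure, but within the general SAE definition.

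**Step 2. Look for text that closes the gap.**

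- The Clavien-Dindo table grades complications by the treatment they require. It has no criterion for admission as such, and its title limits it to surgery-attributed postoperative events, so it does not cover a drug-related admission.
- Outcomes, Secondary, item 3, uses the term SAE without redefining it.
- Appendix A records readmission as a separate variable and does not link it to seriousness.
- The outside reporting guideline may be broader, but its content cannot be read from the documents.

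Nothing in the documents makes a new admission serious in its own right.

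**Step 3. Bound the size.** Inputs:

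- *N* = 88, the enrolment target in Power analysis (44 per group).
- *r* = 30-day readmission rate. The documents give none; 2% to 5% is assumed.
- *f* = share of readmitted women whose event involves serious deterioration but meets no other SAE criterion. Unknown, between 0 and 1.

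Women affected = *N* × *r* × *f*. Setting *f* = 1 gives the upper bound:

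- 88 × 0.02 = 1.76
- 88 × 0.05 = 4.40

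That is at most about 2 to 4 women over both arms. With the 74 women (37 per group) required before the allowance for non-compliance and dropout, the bounds are 74 × 0.02 = 1.48 and 74 × 0.05 = 3.70. Any *f* below 1 lowers these figures in proportion.

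**The case against.** The strongest reply is that this is a wording slip with little consequence. The repeated noun in the criterion suggests that words were lost in drafting. Readmission and reoperation within 30 days and emergency visits are all collected, and emergency visits are already compared between arms, so an analyst could tabulate readmission by arm from the planned dataset. Much of this stands: no safety data are lost. But staff have only this definition to apply, and neither a readmission field nor an emergency-visit count makes an event an SAE.

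A reader might also infer more than the text supports:

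- **That any unplanned overnight stay is an SAE while a readmission never is.** Neither half holds. An overnight stay counts only after serious deterioration, so one for logistics or simple observation does not. A readmission counts if it meets another criterion; venous thromboembolism or pelvic abscess, for example, might do so through preventive intervention, depending on the case.
- **That 2 to 4 SAEs will be missed, perhaps most of the serious events.** The rate is assumed, the figure is a ceiling, and the documents give no expected number of serious events to compare it with.
- **That the comparison between arms is distorted.** The same rule applies to both arms, and investigators, participants and the staff giving follow-up questionnaires are blinded. The omission can lower both counts, but nothing shows that it does so unequally. With so few events the comparison would carry little information under either definition.
- **That urgent safety reports would be missed.** The protocol sets no expedited route. It defers to outside rules that may include admission, and its list of reportable events does not require seriousness. Missed reporting is possible but not shown.

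**Conclusion.** The SAE definition is wrong as written. It treats prolongation of an existing stay as serious and leaves out a new admission, in a population selected for planned same-day discharge. The 30-day SAE outcome may therefore be under-counted in both arms, with classification following the timing of the event relative to discharge rather than its seriousness.

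The size is small in absolute terms: no more than about 2 to 4 of 88 women, resting on an assumed readmission rate of 2–5% and on the extreme case that every readmission involves serious deterioration and meets no other criterion. The conclusion about the wording does not depend on that rate. It does assume that the Adverse Event Definitions section governs the SAE outcome, which is the only reading the documents offer.

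The point deserves correction rather than a note, because a stated rule misclassifies events in a compared outcome and the remedy is simple.

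**What to change.** In Adverse Event Definitions, replace the hospital phrase with: *inpatient hospital admission or prolongation of an existing hospitalisation*. Give it its own bullet, separate from permanent impairment, and keep the serious-deterioration stem so that stays for convenience remain outside.

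Then reconcile the three places that use the concept: state that the SAEs in Outcomes, Secondary, item 3, are those meeting this definition, and that each 30-day readmission recorded under Appendix A is assessed against it.

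The cost is a one-phrase amendment, a cross-reference and possibly a few more events to report. No new assessment is needed and the sample size does not change. Naming 30-day readmission as a secondary outcome in its own right is optional; the gap can be closed without it.
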